1 INTRODUCTION

This supplemental SAP (sSAP) is a companion document to the protocol. In addition to the information presented in the protocol SAP which provides the principal features of confirmatory analyses for this trial, this supplemental SAP provides additional statistical analysis details/data derivations and documents modifications or additions to the analysis plan that are not “principal” in nature and result from information that was not available at the time of protocol finalization.

2 SUMMARY OF CHANGES

sSAP Version #	Protocol Amendment #	sSAP Section # and Name	Description of Change	Brief Rationale
03	03	4.1.1 China-specific Requirements	Added clarifications that PRO is not to be analyzed in China subpopulation	To clarify the PRO analysis for the China subpopulation

3 ANALYTICAL AND METHODOLOGICAL DETAILS

3.1 Statistical Analysis Plan Summary

Key elements of the statistical analysis plan are summarized below; the comprehensive plan is provided in Sections 3.2-3.12.

Study Design Overview	A Phase 3 randomized study of lenvatinib in combination with pembrolizumab versus standard of care in participants with metastatic colorectal cancer who have received and progressed on or after or became intolerant to prior treatment
Treatment Assignment	Approximately 434 participants will be randomized in a 1:1 ratio between two treatment groups: (1) the lenvatinib plus pembrolizumab arm and (2) the SOC arm. Stratification factor is: Presence of liver metastasis (Yes/No). This is an open-label study.
Analysis Populations	Efficacy: ITT Safety: APaT Patient-reported outcome: FAS
Primary Endpoint(s)	Overall survival
Key Secondary Endpoints	Progression-free survival per RECIST 1.1 as assessed by BICR. Objective response rate per RECIST 1.1 as assessed by BICR.

Statistical Methods for Key Efficacy Analyses	The primary hypothesis testing for OS and secondary hypothesis testing for PFS will be evaluated by comparing the experimental group to the control group using a stratified log-rank test. The HR will be estimated using a stratified Cox regression model. Event rates over time will be estimated within each treatment group using the Kaplan-Meier method. The stratified M&N method with strata weighted by sample size will be used for analysis of ORR [1].
Statistical Methods for Key Safety Analyses	For analyses in which 95% CIs will be provided for between-treatment differences in the percentage of participants with events, these analyses will be performed using the M&N method.
Interim Analyses	
Efficacy
 
One interim analysis is planned in this study. Results will be reviewed by an eDMC. Details are provided in Section 3.7.
 
• Interim Analysis:
○ Timing: to be performed after both ~260 OS events have been observed and ~ 7 months after last participant randomized○ Primary purpose: interim efficacy analysis for OS, final analysis for PFS and ORR• Final Analysis:
○ Timing: to be performed after both ~336 OS events have been observed and ~ 7 months after interim analysis○ Primary purpose: final analysis for OS 
Safety
 
An interim safety analysis will be performed and reviewed by the eDMC 6 months after first participant is randomized. Afterwards, the eDMC will review safety data periodically in the study. Details will be specified in the DMC charter.

Multiplicity	The overall type I error over the primary and secondary hypotheses is strongly controlled at 2.5% (1-sided), with 2.5% initially allocated to OS (H1), 0% to PFS (H2), and 0% to ORR (H3). By using the graphical approach of Maurer and Bretz [2], if one hypothesis is rejected, the alpha will be shifted to other hypotheses.
Sample Size and Power	The planned sample size is approximately 434 participants. It is estimated that there will be ~ 336 OS events at the final analysis. With 336 OS events, CCI at an initially assigned 0.025 (1-sided) significance level.
Abbreviations: APaT = all participants as treated; BICR = blinded independent central review; CI = confidence interval; DMC = data monitoring committee; eDMC = external data monitoring committee; FAS = full-analysis set; HR = hazard ratio; ITT = intent to treat; M&N = Miettinen and Nurminen; ORR = objective response rate; OS = overall survival; PFS = progression free survival; SOC = standard of care	

3.2 Responsibility for Analyses/In-House Blinding

The statistical analysis of the data obtained from this study will be the responsibility of the Clinical Biostatistics department of the Sponsor.

The Sponsor will generate the randomized allocation schedule(s) for study treatment assignment as appropriate in this protocol, and the allocation will be implemented in IRT.

This study is being conducted as a randomized, open-label study, i.e., participants, investigators, and Sponsor personnel will be aware of participant treatment assignments after each participant is enrolled and treatment is assigned. Although the study is open label, analyses or summaries generated by randomized intervention assignment, or actual intervention received will be limited and documented.

Blinding issues related to the planned interim analyses are described in Section 3.7.

3.3 Hypotheses/Estimation

Objectives and hypotheses of the study are stated in Section 3 of the protocol.

3.4 Analysis Endpoints

Efficacy and safety endpoints that will be evaluated are listed below.

3.4.1 Efficacy Endpoints

Primary

- Overall Survival**

OS is defined as the time from randomization to death due to any cause.

Secondary

- Progression-free survival**

PFS is defined as the time from randomization to the first documented disease progression per RECIST 1.1 by BICR or death due to any cause, whichever occurs first.

- Objective Response Rate**

The ORR is defined as the percentage of participants who achieve a confirmed CR or PR per RECIST 1.1 as assessed by BICR.

- Duration of Response**

For participants who demonstrate confirmed CR or PR, duration of response is defined as the time from the first documented evidence of CR or PR until disease progression or death due to any cause, whichever occurs first.

3.4.2 Safety Endpoints

Safety and tolerability will be assessed by clinical review of all relevant parameters, including AEs, SAEs, fatal AEs, laboratory tests, and vital signs. Furthermore, specific events will be collected and designated as ECIs as described in Section 8.4.7 of the protocol.

3.4.3 PRO Endpoints

- Change from baseline in EORTC QLQ-C30 global health status/QoL, physical functioning and appetite loss and EORTC QLQ-CR29 bloating scores for the combination of lenvatinib plus pembrolizumab versus SOC
- Time to first deterioration (TTD) in EORTC QLQ-C30 global health status/QoL, physical functioning and appetite loss and EORTC QLQ-CR29 bloating scores for the combination of lenvatinib plus pembrolizumab versus SOC

Based on prior literature (Bjordal, et al., 2000; Osoba D, 1998 [3]; King, 1996 [4]), a 10 points or greater worsening from baseline for each scale represents a clinically relevant deterioration for EORTC. TTD is defined as the time from baseline to the first onset of a 10 or more points deterioration from baseline.

- Change from baseline in **CCI** [REDACTED] for the combination of lenvatinib plus pembrolizumab versus SOC
- **CCI** [REDACTED]

The assessment for possible PRO response at a time point considering subsequent confirmation is defined as follows:

Assessment Category at a time point (one analysis visit)	Change from baseline at a time point (one analysis visit)	Change from baseline at the subsequent time point (the next consecutive analysis visit)
Improvement	score improved from baseline by ≥ 10 points	score improved from baseline by ≥ 10 points
Stability	score improved from baseline by ≥ 10 points	score improved or worsened from baseline by < 10 points
	score improved or worsened from baseline by < 10 points	score improved or worsened from baseline by < 10 points
	score improved or worsened from baseline by < 10 points	score improved from baseline by ≥ 10 points
Worsening	score worsened from baseline by ≥ 10 points	not required
Unconfirmed	A time point assessment that doesn't meet any of the above criteria.	

The overall improvement is defined as the best observed PRO response that is an improvement among all post-baseline assessments by timepoint. The overall improvement + stability is defined as the best observed PRO response that is an improvement or stability among all post-baseline assessments by timepoint.

Changes from baseline in EORTC QLQ-C30 scores will also be interpreted according to recent subscale-specific guidelines, which indicate that clinically meaningful differences vary by scale (Cocks et al., 2012) [5].

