3.6.1.2 Progression-Free Survival

The nonparametric Kaplan-Meier method will be used to estimate the PFS curve in each treatment group. The treatment difference in PFS will be assessed by the stratified log-rank test. A stratified Cox proportional hazard model with Efron's method of tie handling will be used to assess the magnitude of the treatment difference (ie, HR) between the treatment arms. The HR and its 95% CI from the stratified Cox model with a single treatment covariate will be reported. The stratification factors used for randomization (see Section 6.3.2 of protocol) will be applied to both the stratified log-rank test and the stratified Cox model.

Since disease progression is assessed periodically, PD can occur any time in the time interval between the last assessment where PD was not documented and the assessment when PD is documented. The true date of disease progression will be approximated by the earlier of the date of the first assessment at which PD is objectively documented per RECIST 1.1 by BICR and the date of death. Death is always considered a PD event. Surgical participants (i.e., those who undergo oncologic surgeries with curative intent) will be followed to the disease recurrence after the surgery for PFS analysis.

For the primary analysis, any participant who experiences an event (PD or death) immediately after 2 or more missed disease assessments will be censored at the last disease assessment prior to the missed visits. In addition, any participant who initiates new anti-cancer therapy prior to documented progression will be censored at the last disease assessment prior to the initiation of new anti-cancer therapy. Participants who do not start new anti-cancer therapy and who do not experience an event will be censored at the last disease assessment. If a participant meets multiple criteria for censoring, the censoring criterion that occurs earliest will be applied.

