3.6.3.2 PRO Completion and Compliance Summary

Completion and compliance of EORTC QLQ-C30, EORTC QLQ-CR29, and EQ-5D by visit and by treatment will be described. Numbers and percentages of complete and missing data at each visit will be summarized.

Completion rate of treated participants (CR-T) at a specific visit for a given instrument is defined as the number of treated participants who complete at least one item on that PRO instrument over the number of treated participants in the PRO analysis population.

$$\text{CR-T} = \frac{\text{Number of treated participants who complete at least one item}}{\text{Number of treated participants in the PRO analysis population}}$$

The completion rate is expected to decrease at later visits during study period for reasons such as study design (e.g., PROs not required following progression), patient discontinuation, etc. Therefore, the compliance rate (CR-E) will also be presented in addition to completion rate. CR E is defined as the number of treated participants who complete at least one item of the instrument over number of participants who are expected to complete the PRO assessment at that visit, excluding participants missing by design such as death, discontinuation, translation not available.

$$\text{CR-E} = \frac{\text{Number of treated participants who complete at least one item}}{\text{Number of treated participants who are expected to complete}}$$

The completion and compliance status will be summarized as below:

- Completed as scheduled
- Not completed as scheduled
- Off-study: not scheduled to be completed.

The reasons for non-completion as scheduled of these measures are collected using “miss_mode” forms filled by site personnel and will be summarized in a table format. The schedule (study visits and estimated study times) and mapping of study visit to analysis visit for PRO data collection is provided in [Table 5](#).

Table 5 PRO Data Collection Schedule and Mapping of Study Visit to Analysis Visit

Treatment Week	Week 0	Week 2	Week 4	Week 6	Week 8	Week 10	Week 12	Week 16	Week 20	Week 24	Week 28
Day	1	15	29	43	57	71	85	113	141	169	197
Range (relative day to first dose date)	[-5, 8]	[9, 22]	[23, 36]	[37, 50]	[51, 64]	[65, 78]	[79, 99]	[100, 127]	[128, 155]	[156, 183]	[184, 211]
Treatment Week	Week 32	Week 36	Week 40	Week 44	Week 52	Week 60	Week 68	Week 76	Week 84	Week 92	Week 100
Day	225	253	281	309	365	421	477	533	589	645	701

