3.6.3.3 Change from Baseline

The time point for the mean change from baseline analysis is defined as the latest time point at which CR-T $\geq 60\%$ and CR-E $\geq 80\%$, and week 8 was selected based on blinded data review prior to the database lock for any PRO analysis.

To assess the treatment effects on the PRO score change from baseline in the EORTC QLQ-C30 global health status/QoL, physical functioning and appetite loss, EORTC QLQ-CR29 bloating scores, and EQ-5D-5L VAS, a constrained longitudinal data analysis (cLDA) model proposed by Liang and Zeger [8] will be applied, with the PRO score as the response variable, and treatment, time, the treatment by time interaction, and the stratification factors used for randomization (see Section 6.3.2 of protocol) as covariates. The treatment difference in terms of least square mean change from baseline will be estimated from this model together with 95% CI. Model-based least square mean with 95% CI will be provided by treatment group for PRO scores at baseline and post-baseline time point.

The technical details on the cLDA model are in the appendix of this sSAP.

Line plots for the empirical mean change from baseline in EORTC QLQ-C30 global health status/QoL, physical functioning and appetite loss, EORTC QLQ-CR29 bloating scores, and EQ-5D-5L VAS score will be provided across all time points as a supportive analysis.

In addition, the model-based LS mean change from baseline to the specified post-baseline time point together with 95% CI will be plotted in bar charts for EORTC QLQ-C30 global health status/QoL scores, all functioning and symptom scores, and for EORTC QLQ-CR29 all functioning and symptom scores.

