3.6.3.4 Time-to-First-Deterioration

The Kaplan-Meier method will be used to estimate the TTD curve for each treatment group. The estimate of median time to deterioration and its 95% confidence interval will be obtained from the Kaplan-Meier estimates. The treatment difference in TTD will be assessed by the stratified log-rank test. A stratified Cox proportional hazard model with Efron's method of tie handling and with a single treatment covariate will be used to assess the magnitude of the

treatment difference (ie, HR). The HR and its 95% CI will be reported. The stratification factors used for randomization (see Section 6.3.2 of protocol) will be used as the stratification factors in both the stratified log-rank test and the stratified Cox model.

The approach for the TTD analysis will be based on the assumption of non-informative censoring. The participants who do not have deterioration on the last date of evaluation will be censored. [Table 6](#) provides censoring rule for TTD analysis.

Table 6 Censoring Rules for Time to First Deterioration

Scenario	Outcome
Deterioration documented	Event observed at time of assessment (first deterioration)
Ongoing or discontinued from study without deterioration	Right censored at time of last assessment
No baseline assessments	Right censored at treatment start date

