3.6.3.5 Overall Improvement / Overall Improvement and Stability

Overall improvement rate will be analyzed, which is defined as the proportion of participants who have achieved an overall improvement as defined in Section 3.4.3 PRO Endpoints. Stratified Miettinen and Nurminen's method will be used for comparison of the overall improvement rate between the treatment groups. The difference in overall improvement rate and its 95% CI from the stratified Miettinen and Nurminen's method with strata weighting by sample size will be provided. The stratification factors used for randomization (See Section 6.3.2 of protocol) will be applied to the analysis.

The point estimate of overall improvement rate will be provided by treatment group, together with 95% CI using exact binomial method by Clopper and Pearson (1934) [\[6\]](#).

The same method will be used to analyze overall improvement and stability rate, which is defined as the proportion of participants who have achieved overall improvement and stability as defined in Section 3.4.3 PRO Endpoints.

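### Do the overall improvement and improvement-plus-stability rates need an adjustment for unequal length of PRO collection?

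*SAP*

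**What the plan says.** Section 3.4.3 classifies each visit as improvement, stability, worsening or unconfirmed. Improvement and stability need support from the next consecutive analysis visit. The participant-level result is then the best category reached: "The overall improvement is defined as the best observed PRO response that is an improvement among all post-baseline assessments by timepoint"; the second rate is the "best observed PRO response that is an improvement or stability among all post-baseline assessments". No visible text sets a common window or a minimum number of assessments.

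Section 3.6.3.5 says that the stratified Miettinen and Nurminen "method will be used for comparison of the overall improvement rate between the treatment groups", with a 95% confidence interval. The same method serves improvement plus stability.

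Three other places bear on the point:

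- Section 3.6.3.2 explains falling completion by reasons such as study design, with the example "PROs not required following progression". It plans completion and compliance tables per visit and per arm, with numbers complete and missing.
- For mean change, section 3.6.3.3 says "week 8 was selected based on blinded data review prior to the database lock for any PRO analysis".
- For time to first deterioration (TTD), Table 6 in section 3.6.3.4 gives "Right censored at time of last assessment" for participants without deterioration, and the text adds "The approach for the TTD analysis will be based on the assumption of non-informative censoring".

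One bullet in section 3.4.3, directly before the response categories, is redacted. So is the last row of Table 7, which follows the rows for mean change and TTD.

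**The concern.** A best-ever rate can only rise with the number of visits. Because of the confirmation rule, a participant needs at least two post-baseline assessments to count at all. If collection stops at progression and progression comes later on the experimental arm, that arm gets more chances even when scores behave identically in both arms. The mean-change analysis has a fixed time point and TTD has censoring; these two rates have neither in the visible text. Of the 21 post-baseline visits in Table 5, 17 fall after week 8.

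At stake is the reading of a nominal comparison: a difference in the rates could be taken for a quality-of-life effect when part of it is length of collection. The natural request would be a supportive time-to-improvement analysis and assessment counts by arm.

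**Working it through.** **1. The plan's own figure.** The assumed PFS effect drives the expected imbalance. With 404 events and hazard ratio 0.65 (Table 10), power = Φ(|ln 0.65| × √404 / 2 − z). Here 0.4308 × 10.050 = 4.329.

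- One-sided alpha 0.0125: Φ(4.329 − 2.2414) = Φ(2.088) = 0.9816 (Table 10: 0.9820).
- One-sided alpha 0.025: Φ(4.329 − 1.9600) = Φ(2.369) = 0.9911 (Table 10: 0.9912).

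**2. Implied control PFS median.** Inputs are 404 events among 434 participants at month 18, 11 months of enrolment with a 2-month ramp (taken as linear), exponential PFS and hazard ratio 0.65. The median is 2.22 months with no dropout, 1.83 with an assumed 1% per month and 1.48 with 2% per month. A median of 3.0 months gives only about 378 events and so does not fit the plan.

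**3. Size of the artefact with no PRO effect.** The SAP gives none of these inputs, so they are assumptions: person mean N(65, 18), visit error SD 12 or 15, scores in steps of 100/12, 90% compliance, and confirmation at the next scheduled visit. Visits are those of Table 5. The 8-week scan interval is also assumed; section 3.6.1.2 gives only "Since disease progression is assessed periodically". Results for a control median of 2.2 months, in per cent, control v experimental, SD 12 / SD 15:

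| Scenario | Improvement | Improvement plus stability |
|---|---|---|
| Progression found at scans, stable scores | 22.8 v 25.2 / 27.8 v 30.8 | 83.4 v 85.9 / 79.5 v 82.4 |
| Same, equal decline of 3 points/month | 13.5 v 13.9 / 19.1 v 19.9 | 73.7 v 75.1 / 70.5 v 72.1 |
| Scans, other discontinuation 1% v 2%/week | 20.9 v 20.8 / 25.9 v 25.6 | 78.7 v 76.2 / 75.0 v 72.6 |
| Scans, other discontinuation 1% v 3%/week | 20.9 v 19.1 / 25.7 v 23.5 | 78.8 v 71.8 / 74.8 v 68.3 |
| Collection stops at progression itself | 15.7 v 19.7 / 19.3 v 24.2 | 59.2 v 68.6 / 56.1 v 65.8 |

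In the first row the mean number of assessments is 6.3 v 7.7, so most of the 17 late visits are seldom reached.

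**4. Set against precision.** Assume 200 per arm in the PRO population (217 per arm are randomized).

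- Improvement, first row, SD 12: half-width = 1.96 × √(0.228 × 0.772/200 + 0.252 × 0.748/200) = 8.4 points; gap 2.4.
- Improvement plus stability, same row: half-width 7.1 points; gap 2.5.
- Improvement plus stability, last row, SD 12: half-width 9.4 points; gap 9.4.

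The gap is therefore as large as the half-width only if collection ends at progression itself. It comes close at 3% per week discontinuation: −7.0 against 8.4.

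**5. Is a stated rule wrong?** The target is the proportion of participants who show a confirmed improvement while under PRO collection. Someone who progresses before showing one has not improved in that sense. That is a coherent composite, and Table 3 treats ORR similarly by counting participants with missing data as non-responders. Miettinen and Nurminen is valid for such a proportion. The rates are outside the alpha-controlled hypotheses of section 3.8, and section 3.6 asks for caution with nominal p-values.

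**6. Would the extra analysis settle the matter?** Time to first confirmed improvement, censored at the last assessment, gives hazard ratios of 0.99 to 1.01 in simulation, but only because scores were made independent of progression. If scores fall 10 to 15 points in the 4 weeks before progression, its hazard ratio is 1.08 to 1.27. It would also leave improvement plus stability, which has the larger gaps, untouched.

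**The case for a change.** The strongest opposing case is that the mechanism follows from the plan's own assumptions. With collection stopping at progression and hazard ratio 0.65, simulated gaps are 4 to 7 points for improvement and 7 to 11 for improvement plus stability. The 95% interval then excludes zero in favour of the experimental arm in 15 to 39% and 34 to 62% of trials, against a nominal 2.5%. With a PFS hazard ratio of 1 the gap vanishes. Confirmation does not help, and time to improvement dated at the confirming visit rejects in 2.2%.

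The dependence on length of collection stands. Even the scan-based gap is not nil: 2.4 points is 2.4/4.27 = 0.56 standard errors, which raises the one-sided chance from 2.5% to about 8% (1 − Φ(1.40)). For improvement plus stability, 2.5/3.60 = 0.69 gives about 10%.

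Two parts do not carry over. The high rejection rates belong to the extreme case only. The SAP does not say whether collection ends at progression on a scan, at treatment discontinuation or at a later visit, and it mentions progression only as an example of why completion falls. Also, these are false positives only if the target is the score trajectory alone. For the composite as defined, the proportions really do differ.

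Assessment counts per participant would be somewhat more direct than the planned tables, but mean assessments per arm already follow from the numbers complete at each visit.

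**Conclusion.** The concern does not hold as a fault in the plan. Both rates depend on how long PROs are collected, as any best-ever rate does, but nothing in sections 3.4.3 or 3.6.3.5 is wrong, contradictory or badly fixed. In the scan-based case with stable scores, the part of the difference due to collection length is about 2 to 3 points, inside a half-width of roughly 7 to 9. It shrinks to +0.2 to +0.9 (improvement) and +0.6 to +1.8 (improvement plus stability) under an equal decline of 3 to 5 points per month. It turns negative for improvement plus stability once discontinuation for other reasons is higher on the experimental arm.

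These sizes rest on assumed scan interval, score variability, compliance and discontinuation. Gaps of 8 to 11 points in improvement plus stability arise only if collection ends at progression itself. The redacted Table 7 row sits where the method and missing-data approach for these rates would be stated, so the absence of an allowance cannot be asserted. A time-to-improvement analysis is a matter of preference: it has a different estimand, its own link to PFS, and no coverage of the rate most affected. No change is needed. A reader of the results should view these rates beside the planned completion tables.
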